Patients will undergo dynamic, first pass, stress perfusion imaging during maximal hyperemia induced with Lexiscan™. Imaging will commence approximately 90 seconds after a bolus of Lexiscan™ (0.4 mg per each 5 mL injection). The Lexiscan™ is followed immediately by a bolus of 10 cc saline. In order to achieve the correct timing of the dynamic image acquisition, contrast administration will begin approximately 80 seconds after the Lexiscan™ bolus to allow the contrast to reach the heart at the moment of maximal hyperemia. Data will be acquired for 30 seconds with both X-ray tubes set at 80 – 100 kV, a gantry rotation time of 0.28 seconds, and a tube current of 300 mAs per rotation. Temporal resolution is approximately 75 ms. Patients will be instructed to hold their breath for the first 15 seconds of the scan, as this is the most important portion of the data acquisition for quantifying myocardial blood flow. They will then be instructed to breath shallowly for the remaining 15 seconds. Perfusion imaging is performed in an ECG-triggered shuttle mode in which the table shifts between two z-positions of the heart to allow coverage of nearly the entire left ventricle. End systolic imaging is used to reduce motion artifacts, to image the heart at its smallest dimensions, and to reduce beam-hardening artifacts from contrast in the LV cavity. The relatively fast rotation time combined with the dual source system gives markedly improved temporal resolution, which helps to reduce motion artifacts associated with the rise in heart rate that frequently occurs after Lexiscan™ administration. With a detector width of 38 mm and 10% overlap between the two imaging positions, the coverage of the acquisition is 73 mm. In some patients, small portions of the base or apex could be cut off. A total of 14 or 15 image volumes during myocardial passage of the contrast bolus will be acquired. CT MPI studies will use 40 – 50 mL of contrast agent (Ultravist 370) administered at a flow rate of 4 – 6 mL/s. Following the perfusion imaging, the Lexiscan™ will be

reversed with 1 mg/kg of aminophylline per standard clinical protocol if indicated by the supervising physician.

CT Perfusion Data Reconstruction and Analysis:

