A checklist will be made and each of the following events will be assessed by an investigator or designated personnel:

1. Hypotension (systolic BP < 90 or > 30 mm Hg decrease from baseline)
2. Hypertension (systolic BP > 200 mmHg)
3. Significant new heart block (type II 2nd degree or 3rd degree A-V block)
4. Bradycardia (heart rate < 45 bpm, sinus bradycardia or junctional rhythm)
5. Bronchospasm (requiring inhaler or other medical treatment)
6. Allergic reaction (hives, erythema, wheezing)

7. Chest pain
8. Nausea
9. Headache
10. Seizures

Additionally, a patient satisfaction questionnaire (detailed below) will be administered to all patients who undergo the CT perfusion scan following the research scan as well as a 30-day event rate (MACE defined by ED visit, hospitalization, ACS/MI, stroke, revascularization, significant new arrhythmia and death) will be assessed by chart review and follow-up phone call one month (+/- 3 days) from the scan.

Patient Satisfaction Survey:

Following the CT perfusion scan, the patient will be given a participant satisfaction survey. The purpose of this survey is to assess the patients' subjective experience with the different imaging modalities (CT vs. SPECT/MRI stress perfusion imaging). The seven question survey will assess: 1) the patient's perception of the overall ease or difficulty of the study, 2) length of the study, 3) perceived discomfort, 4) level of apprehension, 5) understanding of the nature of the test, 6) understanding of the results and 7) willingness to undergo the test again. Each question will have a quantitative score of 1 – 4. Patients who have not yet undergone SPECT imaging at the time will be asked the SPECT specific questions at the time of the 30-day follow-up if they have undergone the SPECT testing at that time. If not, the patient will not be asked the SPECT questionnaire.

D.2 STATISTICAL METHODS / SAMPLE SIZE JUSTIFICATION

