Common side effects of the drug Nitroglycerine (a Nitrate available in 0.4 mg or 0.8 mg for sublingual (under the tongue) administration include headache which may be severe and persistent and may occur immediately after use. Vertigo, dizziness, weakness, palpitation (irregular beatings of the heart), and other symptoms of postural hypotension (low blood pressure) may develop occasionally, particularly in upright, motionless subjects. Fainting, which may lead to falls and injuries has also been reported. Flushing, drug rash, and flaky skin have been reported in subjects receiving nitrate therapy.

Use of Regadenoson

The following reactions are listed as warnings and precautions when using regadenoson (Lexiscan™, injected as a 0.4 mg bolus): myocardial ischemia, sinoatrial and atrioventricular nodal block, hypotension, and bronchoconstriction. The following adverse reactions associated with regadenoson are considered transient and are listed in the package insert: dyspnea or urge to breathe deeply, headache, flushing, chest discomfort, angina pectoris or ST segment depression, lightheadedness/dizziness, chest pain, nausea, abdominal discomfort, impaired taste, and feeling hot. Dyspnea can occur during stress myocardial perfusion imaging with associated arrhythmias such as hypoxia induced bundle branch block. The first signs of these rare side effects will cause the termination of the examination.

CT Examination performed with the new Force scanner

The Siemens SOMATOM™ Force is a new computed Tomography X-ray system, which is substantially equivalent to the previous systems (SOMATOM™ Definition and the SOMATOM™ Definition Flash). The SOMATOM™ Force scanner received 510(k) FDA-approval for clinical use on the 17th April 2014.

The SOMATOM™ Force scanner has been used for two other research studies with excellent results. The risks associated with this CT scanner are comparably low to other CT scanners.

Acquisition of patient information

The risks associated with gathering this information are believed to be very low. This information will be stored on a password-protected computer and network server and in a locked office (ART Cardiac Imaging Research Office). The data from this study will be accessible only to the team of researchers from this application.

E.2 ADEQUACY OF PROTECTION AGAINST RISKS

E.2.a Recruitment and Informed Consent

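### The acute checklist gives no rate for 6 of the 11 transient regadenoson reactions the protocol lists, dyspnea foremost; secondarily, the 30-day MACE needs a planned/unplanned flag

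*Combined protocol and SAP*

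**What the plan says.** **Acute reactions.** D.1, Safety and Tolerability Assessment, states: "A checklist will be made and each of the following events will be assessed by an investigator or designated personnel". Ten named events follow: hypotension, hypertension, significant new heart block, bradycardia, bronchospasm needing treatment, allergic reaction, chest pain, nausea, headache and seizures. There is no item for other events.

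**What the protocol expects the drug to do.** E.1.c, Use of Regadenoson, first names warnings: ischemia, sinoatrial and AV nodal block, hypotension and bronchoconstriction. It then lists transient reactions, starting with "dyspnea or urge to breathe deeply, headache, flushing, chest discomfort, angina pectoris or ST segment depression, lightheadedness/dizziness" and continuing with five more: pain in the chest, nausea, discomfort in the abdomen, altered taste and a hot feeling. It adds: "Dyspnea can occur during stress myocardial perfusion imaging with associated arrhythmias such as hypoxia induced bundle branch block". And then: "The first signs of these rare side effects will cause the termination of the examination".

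**Where breathing matters for the scan.** D.1, CT myocardial perfusion protocols: "Patients will be instructed to hold their breath for the first 15 seconds of the scan, as this is the most important portion". The same section says that the drug may be "reversed with 1 mg/kg of aminophylline per standard clinical protocol if indicated by the supervising physician". Under Pharmaceutical Stress Protocol, an EKG is obtained and read after the injection.

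**30-day events.** The outcome is "MACE defined by ED visit, hospitalization, ACS/MI, stroke, revascularization, significant new arrhythmia and death", collected by chart review and a telephone call about one month after the scan. Under Patient Satisfaction Survey, patients who have not yet had SPECT are to be "asked the SPECT specific questions at the time of the 30-day follow-up if they have undergone the SPECT testing" by then.

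**Purpose and reporting.** D.2 names feasibility, safety and tolerability as the main purpose and promises rates with 95% confidence intervals.

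**The concern.** For a single vasodilator bolus, tolerability is largely a matter of its acute symptoms. The protocol lists those symptoms in its risk section but does not carry most of them into the data collection. A listed item can be reported as a rate with an interval, as D.2 promises. A reaction with no item has no planned numerator. If it is not recorded on the day, it may not be recoverable later.

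Dyspnea matters most because it touches two aims. It is a tolerability outcome, and a breathless patient may not complete the 15-second breath-hold that the flow measurement depends on, which is a feasibility outcome. E.1.c also links dyspnea with arrhythmia to ending the exam, yet a stopped exam has no field.

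The 30-day outcome raises a separate, lesser question. It counts any emergency visit, admission or revascularization. Patients come from the emergency department, hospital and clinic, and many are scanned because CTA showed a stenosis. With no control arm, an unflagged rate cannot tell a reader how much is expected care and how much could be harm.

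**Working it through.** **Step 1: the count.** The plan states no rate, power or target for these outcomes, so there is no figure of its own to reproduce. Splitting the transient list in E.1.c at its commas gives 11 entries. Each is set against the 10 checklist items in D.1.

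| Reaction in E.1.c | Nearest checklist item | Match |
|---|---|---|
| Headache | Headache | By name |
| Nausea | Nausea | By name |
| Chest pain | Chest pain | By name |
| Chest discomfort | Chest pain | By meaning |
| Angina or ST depression | Chest pain | By meaning; the ST half has no item |
| Dyspnea | Bronchospasm, only if treated; wheezing under allergic reaction | Only by a stretch |
| Flushing | Erythema, under allergic reaction | Only by a stretch |
| Dizziness | Hypotension, a blood-pressure threshold | Only by a larger stretch |
| Abdominal discomfort | None | No |
| Impaired taste | None | No |
| Feeling hot | None | No |

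**Step 2: sensitivity to the mapping.**

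- Names only: 11 − 3 = 8 unmatched (8/11 = 73%).
- Add chest discomfort: 7.
- Add angina (the natural mapping): 6 (6/11 = 55%).
- Add dyspnea through bronchospasm or wheezing: 5.
- Add flushing through erythema: 4.
- Add dizziness through hypotension: 3 (3/11 = 27%).

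At 5 or fewer, dyspnea counts as covered only by equating it with bronchospasm or wheezing. Transient dyspnea without wheeze or treatment is still not recorded. These percentages count list entries. They are not rates of reactions in patients and do not measure bias.

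**Step 3: other routes to the same data.**

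- E.2.b: side effects are monitored and treated; no recording rule is set.
- E.1.b: progress notes, medication records and vital signs are obtained; no reaction outcome is named.
- E.5: reporting to the IRB is tied to unanticipated problems, and these reactions are anticipated.
- Patient survey (D.1 and Appendix): general questions on discomfort, difficulty, nervousness and willingness to repeat; no symptom is named.

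None of these gives a pre-specified rate for a named reaction.

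**Step 4: the 30-day outcome.** It has 7 components, and none has a planned/unplanned qualifier. Set against it:

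- D.1 expects patients with a stenosis on clinical CTA to be referred for SPECT or catheterization, and speaks of catheterization done clinically after the research scan.
- The survey rule allows SPECT to take place before the 30-day call, and also allows that it has not.
- D.2 expects catheterization data in about 15 of 30 scanned (50%). No date is given for those procedures.
- Neither SPECT nor catheterization is a MACE component. Each adds to MACE only through an emergency visit, an admission or a revascularization.
- Exclusion criterion 17 covers PCI or CABG between the imaging studies. It does not cover revascularization after the last of them.

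Overlap with the 30-day window is therefore possible but not scheduled. The 15 of 30 is a planning figure for available comparisons, not a MACE count, so no confidence interval belongs on it. D.2 works with 30 scanned while enrollment is 100, and the documents do not reconcile the two. The counts in Steps 1 and 2 depend on neither number.

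**The case against.** The strongest case for the plan has five parts.

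**The serious reactions are covered.** Hypotension, high-grade AV block and bronchospasm have items. Sinoatrial block is approached through bradycardia, and ischemia through chest pain and the 30-day ACS/MI component. This stands. A reader might infer that safety monitoring is absent or that serious harm would go unrecorded. The documents do not support that: a cardiologist supervises each injection and reads the EKGs. The gap lies in systematic recording of labelled, transient reactions.

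**The source data largely exist.** Medication records should show aminophylline, the EKGs are read, and dose data are collected for each acquisition. The survey is a planned tolerability measure for every scanned patient. This stands as partial cover. It leaves the reactions without a defined outcome.

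**The count depends on the mapping.** It does, hence the range of 3 to 8. Altered taste and a hot feeling matter less than dyspnea or dizziness. The argument rests on dyspnea, not on the percentage.

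**The form is not in the documents.** It may contain a field for other events. The point therefore concerns the list as the protocol prints it.

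**The MACE point is thin.** Work-up is undated, outpatient tests add nothing to MACE, patients enrolled after SPECT or MRI have already had that test, and a stay under way at the scan is arguably not an event counted from the scan. All of this stands. It reduces the point to a reporting clarification.

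**Conclusion.** The checklist gap is real and should be fixed. On the natural mapping, 6 of 11 listed transient reactions have no item (range 3 to 8), and neither do ST change, an exam stopped early, or other events. Followed as written, the plan would report its main aim without a rate for these. Rates for the listed items are not biased by the gap.

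The MACE flag is a lesser, low-cost addition. Two stronger readings are tempting and should be resisted. One is that work-up is planned inside the 30-day window; no catheterization date is given, so this is only an inference. The other is that up to half of the scanned patients would have work-up-driven events; the 15 of 30 describes catheterization data, not admissions or revascularizations. The all-event rate does not hide harm and no decision rule rests on it. What is lost is the ability to interpret it.

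Assumptions: the printed list is what will be collected, and the sentence on ending the exam refers to dyspnea with arrhythmia, not to dyspnea alone.

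**What to change.** **Checklist.** Add dyspnea, dizziness and flushing, then the remaining E.1.c reactions, and a field for other events. Record ST or new conduction change on the post-injection EKG already being read, whether aminophylline was given, and whether the exam was stopped early and why. This concerns recording only; no treatment or stopping rule changes.

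**30-day MACE.** Keep the all-event rate as defined and report every component separately. By a written rule, have the existing investigators flag each emergency visit, hospitalization and revascularization as (i) scheduled before the scan or already under way at it, (ii) elective after the scan, or (iii) unplanned. Unclear events count as unplanned. No event is removed from the safety result.

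**Cost.** Protocol wording, a few case report form fields and a short classification step; no new visit, procedure or assessor. The downsides are some judgment in the flag, limited by keeping the all-event rate, and probably a higher reported reaction rate.

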Patients who have been referred for a coronary CTA performed as part of a standard clinical evaluation determined by the treating physician(s) will be eligible for the study and recruited from the MUSC CT schedule. Before the patient comes in for their clinical coronary CTA, their cardiologist or primary physician will be contacted to ensure patient interest in the study and willingness to be approached. Willing patients will be approached and will undergo the informed consent process. Consented subjects will first undergo their clinically indicated coronary CTA; if there is no moderate or significant stenosis on the CTA following an initial interpretation (i.e., normal or near-normal coronary arteries), the patient will not undergo the stress CT perfusions portion of the study and will have their usual care without further testing for cardiac ischemia. However, these patients will be included in the data analysis, belonging to the negative CT population (see Patient Flow Chart below). Patients with moderate, indeterminate, or significant stenosis of any major or large branch epicardial vessel on the CTA will then undergo the stress CT perfusion study. According to current guidelines, it

is to be expected that this group of patients will also be clinically referred for further ischemia workup with either SPECT or coronary catheter angiography.

Patients who have undergone SPECT *without* referral for cardiac CTA will also be eligible for this study. For these patients, the coronary CT at rest will be performed as a research procedure followed by the stress portion of the CT perfusion study. No interpretation will be performed before the stress portion of the exam so all of these patients will receive the stress portion of the exam. These patients must have the clinically indicated SPECT as well as the research cardiac CTA with CT perfusion study completed within 60 days.

[figure not shown]
Patients who have undergone SPECT with a prior cardiac CTA will also be eligible for this study. These patients will only undergo the stress portion of CT perfusion study. These patients must have the clinically indicated cardiac CTA and SPECT as well as the research CT perfusion study completed within 60 days.

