Since the examinations in this study are performed for research purposes and are not used for diagnostic purposes, there are no direct benefits for study participants. However, the knowledge gained from this study may benefit future patients undergoing CT myocardial perfusion imaging. Substantial reductions in radiation dose are expected with the new CT systems. Considering that ionizing radiation is thought to carry a small stochastic risk of inducing cancer, the dose reduction further reduces this theoretical risk. Furthermore, because of the higher attenuation of iodine at low photon energies, the novel CT system can be expected to substantially decrease the amount of contrast material required for CT cardiac perfusion examinations. The small risk of compromising renal function by administration of iodinated contrast material in patients with preexisting renal disease can thus be further minimized.

E.4 IMPORTANCE OF THE KNOWLEDGE TO BE GAINED

Knowledge gained during this study will enable an appreciation of the diagnostic accuracy of Ct cardiac perfusion imaging in comparison SPECT and invasive angiography for diagnosis of acute chest pain and give indications of potential impacts on clinical and diagnostic pathways.

Furthermore, data from this study may potentially allow for substantial reductions in radiation dose and contrast material volume of CT examinations with new CT systems thus further minimizing the small risks of radiation-induced cancer and post-contrast nephropathy. Furthermore, the diagnostic value of CT imaging in detection coronary stenosis may be improved.

E.5 SUBJECT SAFETY AND MINIMIZING RISKS (DATA AND SAFETY MONITORING PLAN)

Eligibility in each case will be confirmed by a named investigator. The source data will be collected by an independent technician and/or study coordinator, maintained securely by the PI and checked by the named investigators. Clinical data will be recorded on a Case Report Form (CRF). However, formal monitoring of site records will not be completed as part of the general conduct of the study. Data collected will be authentic, accurate and complete and the study will be conducted in accordance with the currently approved protocol (and any future approved amendments), Good Clinical Practiced (GCP) and all applicable regulatory requirements.

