How willing would you be to undergo the SPECT or MRI stress perfusion procedure again?	(1) Very Willing (2) Somewhat Willing (3) Somewhat Unwilling (4) Not at All Willing

Patient Satisfaction Survey (CT Perfusion Scan)

How easy or difficult did you find the CT Perfusion Scan procedure?	(1) Very Easy (2) Easy (3) Difficult (4) Very Difficult
How do you feel about the length of the CT Perfusion Scan procedure?	(1) Very Short (2) Short (3) Long (4) Very Long
How much discomfort did you experience during the CT Perfusion Scan procedure?	(1) No Discomfort (2) Some Discomfort (3) Moderate Discomfort (4) A Lot of Discomfort

How nervous were you before and during the CT Perfusion Scan procedure?	
(1) Not Nervous
 
(2) Somewhat Nervous
 
(3) Moderately Nervous
 
(4) Very Nervous

How well do you feel that you understand the CT Perfusion Scan procedure?	
(1) Very Much Understand
 
(2) Moderately Understand
 
(3) Somewhat Understand
 
(4) Don't Understand

How well do you feel that you understand the results of the procedure?	
(1) Very Much Understand
 
(2) Moderately Understand
 
(3) Somewhat Understand
 
(4) Don't Understand

How willing would you be to undergo the CT Perfusion Scan procedure again?	
(1) Very Willing
 
(2) Somewhat Willing
 
(3) Somewhat Unwilling
 
(4) Not at All Willing

H. REFERENCES

4. Cury RC, Budoff M and Taylor AJ. Coronary CT angiography versus standard of care for assessment of chest pain in the emergency department. *J Cardiovasc Comput Tomogr*. 2013;7:79-82.

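### As scheduled, the CT versus SPECT/MRI patient survey is open to bias: item 6 asks about CT results not described as available, and the comparator is normally rated later

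*Combined protocol and SAP*

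**What the plan says.** Section D.1, under Patient Satisfaction Survey, gives the survey a comparative aim: "The purpose of this survey is to assess the patients' subjective experience with the different imaging modalities (CT vs. SPECT/MRI stress perfusion imaging". It has seven items, each scored 1 to 4, with one form for CT perfusion and a parallel form for SPECT or MRI (Appendix).

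The timing is set in the same place: "Following the CT perfusion scan, the patient will be given a participant satisfaction survey". One exception is made. Patients who have not yet had SPECT "will be asked the SPECT specific questions at the time of the 30-day follow-up if they have undergone the SPECT testing at that time"; if SPECT has still not been done by then, the SPECT form is not asked. The follow-up itself is by chart review and a "follow-up phone call one month (+/- 3 days) from the scan".

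The sixth item on both forms reads "How well do you feel that you understand the results of the procedure". Section E.3 describes the research scans as follows: "Since the examinations in this study are performed for research purposes and are not used for diagnostic purposes".

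For patients who enter after SPECT without a CTA referral, D.1 sets the permitted gap: "These patients must have the clinically indicated SPECT as well as the research cardiac CTA with CT perfusion study completed within 60 days". The same 60 days is given for the other SPECT and MRI entry routes. The CT Coronary Angiography Protocol part of D.1 gives 30 days for SPECT instead.

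Section D.2 names no analysis, total score or decision rule for the survey. It does carry a general statement that P values of 0.05 or less count as significant.

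**The concern.** A within-patient comparison of two tests needs the same question to mean the same thing for both, and needs the answers to be collected under similar conditions. Neither holds here.

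Item 6 puts a clinical test, done so that its results can be used in care, beside a research scan whose perfusion result the patient has no described way of knowing when the form is given. A worse CT score on that item could reflect the schedule alone.

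For the other items, the CT experience is rated fresh and the comparator normally from memory. Patients who had SPECT or MRI first also rate it with the CT experience already behind them. Discomfort, apprehension, understanding of the test and willingness to repeat it are all open to recall and carry-over. If test and form dates are not collected, these influences cannot be examined afterwards.

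**Working it through.** The plan states no effect size, power or test for the survey, so there is no figure to reproduce. The check sets the schedule side by side and then asks what would cancel.

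**1. Is a CT perfusion result available when item 6 is asked?** D.1 (CT Perfusion Data Reconstruction and Analysis) requires motion correction, a manually defined volume around the ventricle and a deconvolution step; the scans are then read by two readers. In the two routes where the resting CT is a research procedure, nothing is interpreted before the stress scan. E.3 says the research scans do not serve diagnosis. No section describes giving the patient a CT perfusion result. Patients referred for CTA do have an initial CTA reading at the visit, but the form asks about the CT perfusion scan.

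**2. Lag from each test to its form.** Day 0 is the CT perfusion scan. The CT form is assumed to be given at that visit, which the wording implies but does not state. One month is taken as 30 days, so the follow-up falls on days 30 − 3 = 27 to 30 + 3 = 33.

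| Order | CT lag | Comparator lag | Comparator form relative to CT |
|---|---|---|---|
| SPECT or MRI first | about 0 days | 0 to 60 days (0 to 30 for SPECT if the other D.1 window applies) | after CT |
| SPECT after CT | about 0 days | 0 to about 33 days | after CT, at follow-up |

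The first row follows because only patients who have not yet had SPECT are deferred. The others therefore answer both forms after the CT scan.

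**3. What cancels and what does not.** Let δ be the true modality difference (CT minus comparator), o the shift from being the second test, r the shift in the comparator score from delayed recall, and f the share of patients with the comparator first. Then

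expected mean difference = δ + (2f − 1)·o − r.

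The order term is −0.5·o at f = 0.25, zero at f = 0.5 and +0.5·o at f = 0.75. The documents do not give f. The recall term has the same sign in both orders, because the comparator is normally the delayed answer in both, so no mix of patients removes it.

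**4. Sense of scale only.** Suppose someone applied a two-sided paired t-test at 0.05 with no true difference and an uncancelled recall shift of b standard deviations of the paired difference (noncentrality b·√n). D.2 counts 30 patients with CT perfusion, so 30 pairs is the ceiling on that figure; 15 pairs illustrates missing comparator forms. The values of b are assumptions.

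| b | 15 pairs | 30 pairs |
|---|---|---|
| 0.1 | 6.5% | 8.3% |
| 0.2 | 11.2% | 18.5% |
| 0.3 | 19.2% | 35.5% |
| 0.5 | 43.8% | 75.4% |

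These are rates of nominally significant results. They show that modest shifts could matter, not that shifts of this size exist.

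**The case against.** The strongest reply is that little rests on the survey. Tolerability of the CT procedure is assessed by a ten-event checklist and 30-day MACE, neither of which uses the survey. D.2 plans no survey test and no total score, and test order follows clinical care in a feasibility study. All of that stands, and it limits how much the point matters. It does not remove the comparative purpose that D.1 gives the survey.

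Four stronger readings are tempting and are not supported:

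- *That the main hypothesis claims better tolerability than nuclear imaging, so the bias undermines it.* In section A, the comparison with nuclear imaging attaches naturally to radiation dose and speed; safety and tolerability are stated in absolute terms.
- *That item 6 has a calculable effect.* If CT patients all answered 4 and SPECT/MRI patients 1 or 2, the gap on a seven-item mean would be (4 − 2)/7 = 0.29 to (4 − 1)/7 = 0.43 points. The answers are invented, and the protocol defines no seven-item mean.
- *That order is fixed by entry route, with CT second in four routes of five.* This counts routes, not patients. A patient referred for CTA may already have had SPECT, so CT first is typical in that route rather than certain.
- *That the comparator is always recalled weeks later.* The intervals in the table are upper limits. SPECT done the day before CT, or just before the follow-up call, is recalled within days.

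It is also fair to say that the change below does not cure recall lag.

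**Conclusion.** The concern holds in a limited form. Item 6 is not comparable between CT perfusion and SPECT/MRI as scheduled. The remaining items are open to recall and carry-over bias, because the comparator is normally the later answer and is rated after the CT experience. The lag can reach 60 days when the comparator came first (30 for SPECT under the other window) and about 33 days when SPECT came later.

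The amount and, apart from item 6, the direction of the bias cannot be derived from the documents. For item 6 the expected direction is against CT. The conclusion rests on two inferences: that the CT form is completed at the visit, and that no CT perfusion result reaches the patient before it.

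A reader might go further and infer that the survey cannot yield any fair comparison. The documents do not support that: item 6 is one item of seven, and the others can be reported descriptively with order and lag shown.

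**What to change.** - Exclude item 6 from the CT versus SPECT/MRI comparison, or record it as not applicable for CT perfusion.
- For patients who have already had SPECT or MRI, give the SPECT/MRI form at the CT visit before the CT scan, and the CT form after it. This stops the CT experience from colouring the comparator answers.
- Record the date of each test and of each form. Report paired per-item differences descriptively by test order and recall lag, and do not attribute a difference to modality alone.

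The cost is one form moved to earlier in the same visit, one item dropped from a comparison and a few date fields. The comparison falls to six items, and the order subgroups are smaller. Recall lag and non-randomised order remain, which is why the reporting should stay descriptive.
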